3.5 Rationale for Study and Device Use

Percutaneous approaches to treating MR are appealing for their potential to provide sufficient reduction in MR without the risks typically associated with open heart surgery. Additionally, as previously stated, nearly 50% of patients with severe MR are not referred or denied to surgery due to prohibitive risks, and the uncertainty of benefit from surgical repair or replacement. Percutaneous therapy provides an alternative treatment option for these high risk surgical candidates and in those whom medical therapy is suboptimal.

Edwards has developed a catheter-based technique for the delivery of a permanent implant to the mitral valve via a trans-septal access to grasp and approximate the anterior and posterior leaflets, creating a double orifice and thereby reducing MR, much like surgical repair and the MitraClip System procedure. The MitraClip procedure has already been shown to be a viable alternative for high risk MR patients. However, MitraClip treatment is limited to specific anatomies, and often requires multiple devices (at least 40% of cases require ≥ 2 devices^{21, 24, 25}) to treat large regurgitant jets, which adds to clinical risk and increases procedural time. Additionally, MitraClip often leaves significant residual MR as previously discussed. The Edwards PASCAL Transcatheter Mitral Valve Repair (TMVr) System is designed to address some of these limitations, including: a larger implant with wider paddles and independent Clasp control to address complex anatomies and regurgitant jets and to potentially reduce the number of implants required for adequate MR reduction; a Spacer in the center of the implant to act as a filler in the regurgitant orifice for reduction of MR; working length that allows maneuverability even with higher septal puncture heights; ergonomic controls similar to other Edwards transcatheter product lines which are already familiar to many interventional cardiologists.

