9.3 Statistical Analysis

A first analysis will be performed when 30 patients complete 30-day follow-up, and a second analysis when all patients in the primary cohort complete their 30-day follow-up. A pooled analysis of all patients from the primary cohort and additional cohort will also be performed. Descriptive statistics will be presented for all primary and secondary endpoints. For quantitative variables, the mean values, standard deviation, maximum and minimum will be calculated. The 95% confidence interval (CI) for the mean will be calculated when relevant.

For qualitative variables, absolute and relative frequencies are determined. Exact binomial 95% confidence interval for proportions will be calculated when relevant.

For combined and individual clinical endpoints the survival rate (and 95% CI) will be calculated using Kaplan-Meier estimator. Kaplan-Meier survival curves will also be presented when relevant.

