##### Performance:

- Device success: device is deployed as intended and the delivery system is successfully retrieved as intended at the time of the patient's exit from the cardiac catheterization laboratory. Per device analysis.
- Procedural success: device success with evidence of MR reduction  $\leq$  MR2+ at discharge and without the need for a surgical or percutaneous intervention prior to hospital discharge. Per patient analysis.
- Clinical success: procedural success with evidence of MR reduction  $\leq$  MR2+ and without MAEs at 30 days. Per patient analysis.

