## 6. STATISTICAL ANALYSES

### 6.1. General Considerations

a. For continuous variables, summary statistics will include number of observations, mean, median, standard deviation, minimum, maximum, and 95% confidence intervals (based on normal distribution, unless otherwise specified) per table shells.

b. For categorical variables, summary statistics will include counts, percentages, and 95% Clopper-Pearson confidence intervals per table shells. In general, the denominator for the percentage calculation will be based on total number of subjects with evaluable data for a specified time point unless otherwise specified. Subjects with missing data will be excluded from the denominator.

c. Survival analysis techniques will be used to analyze the time-to-event variables. Summaries will include the number of subjects at risk, number of events, and number of subjects with the event. Subjects without events will be censored at their last known event-free time point. If this event-free time point occurs after the analysis time point, the days to event variable will be set equal to the analysis time point so that the subject will be included in the analysis. For subjects who did not have an event or early withdrawal and have not yet completed the analysis visit, they will be censored at their last information date. Time to first event curves will be constructed using Kaplan-Meier estimates and all post procedure results will be summarized with Kaplan-Meier estimates of event rates. Hazard ratios, confidence interval for the hazard ratios, and p-values may also be presented from a Cox proportional hazards model.

d. Descriptive statistics will be provided at each follow-up assessment, including change from baseline to subsequent time point for selected endpoints. Paired (i.e., subjects with available data at both baseline and respective time point) and unpaired data will be presented separately.

e. If insufficient data are available for summary statistics, then data will be provided only as listings.

f. Unless otherwise specified, descriptive analysis will be performed for all data. Nonparametric techniques may be used if the data does not meet the assumptions of parametric tests.

g. All analyses will be performed using SAS® Software version 9.4 or later (SAS Institute, Inc., Cary, NC).

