### Performance:

The device success, procedural success and clinical success will be summarized by counts and percentages.

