#### 7.6. Device Usage and Malfunction

- Total number of study devices implanted
- Reason for additional implant(s) of study devices
- Number of non-study devices used
- Name of non-study device

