#### 7.8. Primary Performance Endpoints

- Device Success (Per Device Analysis)
- Procedural Success (Per Patient Analysis)
- Clinical Success (Per Patient Analysis)

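### Device success is analysed per device, but the only interval the plan names for proportions assumes independent units, so it can be too narrow if some patients receive several devices

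*SAP*

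**What the plan says.** SAP 3.1 (Performance) defines device success by deployment and retrieval at the patient's "exit from the cardiac catheterization laboratory. Per device analysis". SAP 7.8 repeats the unit: "Device Success (Per Device Analysis"). Procedural and clinical success are labelled per patient, so the device unit is deliberate.

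More than one study device per patient is foreseen. SAP 7.6 lists "Total number of study devices implanted" and the reason for any additional implant.

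Three provisions bear on the analysis:

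- SAP 6.3 (Performance), specific to these endpoints: "The device success, procedural success and clinical success will be summarized by counts and percentages". It names no interval.
- SAP 6.1(b), the general rule for categorical variables: "summary statistics will include counts, percentages, and 95% Clopper-Pearson confidence intervals per table shells". The same paragraph says that, in general and unless otherwise specified, "the denominator for the percentage calculation will be based on total number of subjects with evaluable data".
- Protocol 9.3: "Exact binomial 95% confidence interval for proportions will be calculated when relevant".

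The table shells are in a separate document (SAP 10). Neither document states the device-level denominator or mentions correlation between devices in one patient.

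**The concern.** An exact binomial interval treats each counted unit as independent. Two devices placed in one patient share the valve, the operator and the procedure, so their outcomes are likely to be positively correlated. In that case 84 devices carry less information than 84 independent trials, and an interval computed as if they were independent overstates the precision.

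The analysis is descriptive, so the estimate and its interval are the result. The study also has the stated aim of guiding future study designs, which may use this rate and its precision. A related gap is the denominator: the general rule counts subjects, the endpoint counts devices, and nothing says whether attempted or implanted devices are meant.

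**Working it through.** The plan gives no expected device success rate, interval width or performance goal, so there is no figure of its own to reproduce. The check asks what the default interval would do under stated assumptions.

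**Inputs**

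- Patients: 60 in the primary cohort (protocol 7.1, SAP 2.2). With the 50 additional patients of protocol 7.1, 110 in the pooled analysis of protocol 9.3.
- Share with two devices: not given for this device. Protocol 3.5 says treatment with an existing clip "often requires multiple devices (at least 40% of cases require" two or more). Assumed 40%, with 20% and 60% as alternatives, and nobody with three.
- Within-patient correlation ρ: not given. Assumed 0.3, 0.5 and 0.8, with 0 as reference.
- True success rate p: assumed 85–99%.

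**Design effect.** With m devices per patient, DEFF = 1 + ρ(Σm²/Σm − 1).

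- 60 patients: 36 with one device and 24 with two, so Σm = 36 + 48 = 84 and Σm² = 36 + 96 = 132. DEFF = 1 + 0.571ρ = 1.17, 1.29 and 1.46.
- 110 patients: 66 with one and 44 with two, so Σm = 154 and Σm² = 242. The ratio 1.571, and hence DEFF, is the same.

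**Effect on one interval.** Take 80 successes in 84 devices (95.2%). The adjusted interval is Clopper-Pearson with successes and devices both divided by DEFF.

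| ρ | Effective devices | 95% interval | Width (points) |
|---|---|---|---|
| 0 (default) | 84.0 | 88.3–98.7% | 10.4 |
| 0.3 | 71.7 | 87.4–98.9% | 11.4 |
| 0.5 | 65.3 | 86.9–99.0% | 12.0 |
| 0.8 | 57.6 | 86.2–99.1% | 12.9 |

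**Coverage of the default interval.** For a two-device patient, both devices succeed with probability p² + ρp(1−p), exactly one with 2p(1−p)(1−ρ), and neither with (1−p)² + ρp(1−p). Convolving these pairs with the single-device patients gives the exact distribution of the total. Coverage is the probability of the totals whose Clopper-Pearson interval contains p. Averages over p from 85% to 99% in half-point steps:

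| Patients, share with two devices | ρ = 0 | 0.3 | 0.5 | 0.8 |
|---|---|---|---|---|
| 60, 20% | 97.4% | 96.7% | 96.2% | 95.4% |
| 60, 40% | 97.2% | 95.8% | 94.9% | 93.3% |
| 60, 60% | 97.1% | 95.2% | 93.9% | 91.8% |
| 110, 40% | 96.6% | 95.1% | 94.0% | 92.3% |
| 110, 60% | 96.8% | 94.8% | 93.4% | 91.1% |

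A finer or coarser grid moves the 40% rows by at most 0.2 points. In those rows, the lowest coverage at any single rate for ρ = 0.3, 0.5 and 0.8 is 93.3%, 92.0% and 89.8% with 60 patients, and 93.6%, 92.2% and 90.2% with 110.

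**Which remedy works.** For 60 patients, 40% with two devices and p = 95%:

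- A patient-level percentile bootstrap (3,000 simulated trials, 1,000 resamples each) covers only about 90%, 89% and 87% at ρ = 0.3, 0.5 and 0.8. The default interval covers 94.5%, 93.3% and 91.3%. If every device succeeds, the bootstrap interval collapses to 100–100%.
- Clopper-Pearson on the effective sample size, with the design effect estimated from the data and floored at 1, kept coverage at about 94.7% or more at every rate tried from 85% to 99%, for 60 and for 110 patients.

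**The case against.** A reader might infer that the SAP prescribes Clopper-Pearson for device success and that the reported interval will therefore be too narrow. The documents support neither step. The endpoint-specific text in SAP 6.3 promises only counts and percentages. The interval comes from a general rule that defers to shells not available here and takes subjects as its usual denominator, and the protocol adds a when-relevant qualifier. What can be seen is an unspecified device-level analysis whose only named default is unsuitable, rather than a wrong interval already fixed.

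The size is also conditional. The 40% belongs to another device, and protocol 3.5 says the study device is designed to reduce the number of implants needed. The correlation is assumed. Clopper-Pearson is conservative, and at 60 patients that absorbs most of the loss at moderate correlation. Quoting coverage at a single true rate can mislead: for 84 devices at ρ = 0.5 it is 93.3% at a rate of 95%, but 96.5% at both 94% and 96%. Finally, no hypothesis, margin or performance goal depends on the interval, and procedural success is already reported per patient.

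All of this stands, and it limits the point to a conditional one. It does not remove it: neither document handles clustering, and a programmer following the general rule would treat the devices as independent. The conservatism also helps less in the pooled analysis.

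**Conclusion.** The point holds in conditional form. If the default exact binomial interval is applied to the device count, it can be too narrow when some patients receive more than one device and outcomes within a patient are positively correlated. Under the 40% assumption, average coverage at 60 patients is about nominal up to a correlation of 0.5 and falls roughly 1.7 points short at 0.8 (95 − 93.3). At 110 patients the shortfall is about 1.0 point at 0.5 and 2.7 points at 0.8. With one device per patient, or no correlation, there is no loss. Only descriptive precision is affected, so this is a cheap improvement and no threat to the trial's conclusions.

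**What to change.** In SAP 6.3, add three statements for device success:

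1. The device-level denominator. Attempted devices fit the definition best, because a count of implanted devices only would leave out failures to deploy.
2. The 95% interval: Clopper-Pearson on the effective sample size. Divide devices and successes by DEFF = max(1, V_cluster/V_binomial). Here V_cluster = [N/(N−1)]·Σ(sᵢ − mᵢp̂)²/(Σmᵢ)² over N patients with sᵢ successes in mᵢ devices, and V_binomial = p̂(1−p̂)/Σmᵢ. If all devices succeed, or all fail, set DEFF to 1. Do not use a percentile bootstrap.
3. Beside it, the share of patients in whom all attempted devices succeeded, with an ordinary Clopper-Pearson interval.

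The table shells should match. The cost is a few sentences, a small program and a somewhat wider interval: in the 80/84 example, 1.0, 1.6 or 2.5 points wider at correlations of 0.3, 0.5 or 0.8. No new data are needed.

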## 6.2. Handling of Missing Data

All statistical analyses on the functional endpoints will be performed using only those patients with available data required for endpoint analysis. No missing value imputation will be performed.

No imputation will be done if the date variables are completely missing. For partial dates, only adverse event (AE) onset date will be imputed as follows:

- 1) If both month and day are missing
  - a. If the AE onset year is the same year as index procedure then use index procedure date to impute this AE onset date
  - b. Otherwise, assign January 1st for this AE onset date
- 2) If only day is missing
  - a. If the AE onset year and month are the same as the procedure ones then use the index procedure date to impute the AE onset date
  - b. Otherwise, assign '01' as the day for the AE onset date

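### The SAP's missing-data rule can drop patients who die or have already failed from the procedural and clinical success rates, and SAP 6.3 makes no exception

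*SAP*

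**What the plan says.** SAP 6.1(b), on categorical variables, sets a default: "the denominator for the percentage calculation will be based on total number of subjects with evaluable data for a specified time point unless otherwise specified". The next sentence is unqualified: "Subjects with missing data will be excluded from the denominator". SAP 6.2 adds: "No missing value imputation will be performed". It also says that analyses of the functional endpoints "will be performed using only those patients with available data required for endpoint analysis". The SAP does not define functional endpoints, and it labels the success measures as performance endpoints.

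SAP 3.1 defines three primary performance endpoints:

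- **Device success** covers placement of the implant and withdrawal of the catheters. Its definition ends "the delivery system is successfully retrieved as intended at the time of the patient's exit from the cardiac catheterization laboratory. Per device analysis", so no later echo enters into it.
- **Procedural success** needs device success, MR of 2+ or less at discharge, and no surgical or percutaneous intervention before discharge.
- **Clinical success** builds on it: "Clinical success: procedural success with evidence of MR reduction" to 2+ or less, and no MAE, at 30 days.

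On their analysis, SAP 6.3 says only this: "The device success, procedural success and clinical success will be summarized by counts and percentages". It gives no denominator and no rule for failures without an echo. Protocol 9.4 speaks only of minimising missing data.

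**The concern.** Two of the three primary performance endpoints rest on an echo taken after the procedure, and death before the visit is one of the reasons an echo will be absent. For such a patient, missingness is a consequence of a bad outcome. A rule that removes patients with missing data then removes failures, and the success rate rises.

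The study has one arm, so no comparator would share the distortion. One stated objective (protocol 7.2) is to guide the design of future studies, so an inflated rate could be carried into their planning. The term evaluable is not defined for a composite, so two competent analysts could report different primary results from the same data.

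**Working it through.** **The plan's own figure.** The analysis population is 60 (SAP 2.2, protocol 9.1). Protocol 9.1 justifies the size by precedent and gives no alpha, power, expected rate, margin or performance goal, so it cannot be re-derived. The arithmetic that is stated agrees: 20 sites × 3 roll-in patients = 60, and 60 + 60 = 120.

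**Which patients the rule can reach.** The table sets the SAP 3.1 definitions against SAP 6.1(b).

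| Patient | Outcome from the definition alone | Under 6.1(b) if the echo is absent |
|---|---|---|
| Failed device success, or intervention before discharge | Fails procedural, hence clinical, success | Excluded on a literal reading |
| Cardiovascular death or other MAE by day 30 | Fails clinical success | Excluded on a literal reading |
| Death before the discharge echo, after device success and with no intervention | Procedural success does not name death | Excluded |
| Adjudicated non-cardiovascular death before the 30-day echo | Not an MAE, so clinical success is not settled | Excluded |
| Alive, no failed component, echo missed or unreadable | Unknown | Excluded; direction of bias not fixed |

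In the first two rows the outcome is known, but the SAP does not say that a known failed component makes a patient evaluable. In the third and fourth rows no rule applies except the exclusion.

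**Size.** Let N be the number of patients, s the successes, and m the true failures that lack the echo.

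- Failures kept: s/N.
- Failures dropped: s/(N − m).
- Difference: s/(N − m) − s/N = s·m / [N(N − m)], which is positive whenever s and m are positive.

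N = 60 and N = 30 come from SAP 2.2 and SAP 4. N = 110 is the primary 60 plus the additional 50 in protocol 7.1. The values of s and m are assumptions. Intervals are 95% Clopper-Pearson, the SAP's method.

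| N | Failures kept | m | Failures dropped | Difference (points) |
|---|---|---|---|---|
| 60 | 54/60 = 90.0% (79.5–96.2) | 1 | 54/59 = 91.5% (81.3–97.2) | +1.5 |
| 60 | 54/60 = 90.0% (79.5–96.2) | 3 | 54/57 = 94.7% (85.4–98.9) | +4.7 |
| 60 | 48/60 = 80.0% (67.7–89.2) | 1 | 48/59 = 81.4% (69.1–90.3) | +1.4 |
| 60 | 48/60 = 80.0% (67.7–89.2) | 3 | 48/57 = 84.2% (72.1–92.5) | +4.2 |
| 30 | 27/30 = 90.0% (73.5–97.9) | 1 | 27/29 = 93.1% (77.2–99.2) | +3.1 |
| 110 | 99/110 = 90.0% (82.8–94.9) | 3 | 99/107 = 92.5% (85.8–96.7) | +2.5 |

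For example, 54 × 3 / (60 × 57) = 162/3420 = 4.7 points.

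**The case against.** The strongest reply is that most early failures are already known failures. Clinical success requires no MAE by 30 days, cardiovascular death is an MAE, and protocol section 17 classes any death as cardiovascular unless it is unequivocally something else. One failed component settles a composite, so a careful analyst would call such a patient evaluable. Both definitions ask for evidence of MR reduction, which supports reading no evidence as no success. SAP 6.1(b) is also hedged, and the table shells, a separate second part of the SAP (section 10), may fix denominators. They were not available for this review.

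This shows that exclusion is not certain for every failure. It does not show that the SAP prevents it. The hedge in 6.1(b) is not taken up in 6.3, and two kinds of death in the table have no rule at all. Elsewhere the SAP does write such rules: a walk not done for a medical reason scores zero (6.4), and the FDA device success definition requires the patient to be alive (6.6).

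A reader might infer more than the documents support:

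- **That all primary results are inflated.** Device success needs no later echo, and primary safety uses Kaplan-Meier. All-cause mortality is also analysed by Kaplan-Meier (SAP 6.4), so early deaths remain visible elsewhere.
- **That surgery or device removal means no echo.** Under protocol 7.8.7.11, a patient who receives no device stays until the 30-day visit, and an explanted patient stays until 30 days after explant. Either may have the echo. Only death necessarily prevents it.
- **That SAP 6.2 compels the exclusion.** Its available-data sentence covers an undefined class of endpoints.
- **That every missing echo inflates the rate.** Assume 60 patients: 52 successes, 3 failures seen on echo, 2 deaths, and 3 living patients without an echo. Dropping all five without an echo gives 52/55 = 94.5%. Counting the deaths as failures gives 52/57 = 91.2%, and counting all five gives 52/60 = 86.7%. Only the first step, 3.3 points, reflects deaths. The full 7.8 points is a worst-case bound, because the three living patients might be successes.

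**Conclusion.** The point holds for procedural and clinical success. Read as written, SAP 6.1(b) can remove patients who die, or who already fail a component, before the required echo, and SAP 6.3 does not override it. Each such failure removed raises the rate by about 1.5 points at N = 60 and about 3 points at N = 30, for true rates of 80% to 90%. These sizes rest on assumed success counts and assumed numbers of failures without an echo, since the documents supply neither. They also take N as the planned 60, although the primary analysis uses the per-protocol population, which may be smaller.

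The effect is on descriptive estimates and their intervals. No hypothesis or performance goal is stated, so type I error is not at issue. The conclusion would soften if the table shells set the denominator, but the SAP text should still agree with them.

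**What to change.** Add to SAP 6.3, stated to override 6.1(b):

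> For procedural and clinical success, a patient who fails any component of that endpoint as the protocol defines it (for procedural success: device success, or intervention before discharge; for clinical success: procedural success, or an MAE by 30 days), or who dies of any cause before the required echo, stays in the denominator as a non-success whether or not an echo exists. The number of living patients with no evaluable echo and no failed component is reported, with a sensitivity analysis counting them as non-successes.

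This keeps the protocol's components. It does not make every MAE a procedural failure or every re-intervention a clinical failure. Counting a death before the echo as a non-success fits definitions that require evidence of MR reduction.

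Also reconcile the MAE definitions. Protocol section 17 lists cardiac mortality and non-elective cardiovascular surgery for device-related complications. Protocol 7.5 and SAP 3.1 list cardiovascular mortality and re-intervention for such complications. The choice decides who is a known failure.

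**Cost.** The denominator rule needs only SAP wording. Reconciling the MAE text touches the protocol and so needs an amendment under its section 14. The reported rates may be a few points less favourable.
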